2.1. Study Rationale

Study I6T-MC-AMBX (AMBX) will assess the pharmacokinetics (PK), safety, and tolerability of a 300-mg subcutaneous (SC) dose of mirikizumab (LY3074828). **CCI**

██████████ solution formulation administered using investigational manual pre-filled syringe (PFS) (1- and 2-mL) or investigational autoinjector (AI) (1- and 2-mL). Both devices will be evaluated at 3 different injection sites (arm, thigh, and abdomen) in order to expand the options for administration in patient use. **CCI**
██████████

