2.2.4. Pharmacokinetics

Studies in healthy participants and participants with psoriasis, UC, or CD found that systemic exposure of mirikizumab increases in proportion to dose, and that mirikizumab has a half-life of approximately 10 days and SC bioavailability of 40%.

Studies AMAR and AMBE compared the PK of mirikizumab following SC delivery of mirikizumab using PFS versus AI. Following administration of 250 mg mirikizumab delivered as 1 x 2-mL AI, geometric least squares (LS) mean AUC from time zero to infinity (AUC[0- ∞]) and maximum observed drug concentration (C_{max}) increased 5% and 19%, respectively, relative to the same mirikizumab dose delivered as 2 x 1-mL PFS. Following administration of 125 mg mirikizumab delivered as 1 x 1-mL AI, geometric LS mean AUC(0- ∞) and C_{max} increased 12% relative to the same mirikizumab dose delivered as 1 x 1-mL PFS. In both studies, no differences in median time to maximum observed drug concentration (t_{max}) of mirikizumab were noted between treatment arms.

Exposure by injection location in study AMBE demonstrated statistically significant differences (that is, the 90% confidence interval [CI] for the ratio of geometric LS means excluded unity) when comparing the 2 administration methods:

- PFS and AI administration into the abdomen
 - exposure increased by up to 62% following administration using the AI compared to PFS.

Overall, the mirikizumab PK is expected to be similar for AI and PFS devices based on the results of these exploratory parallel-group studies.

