4.2. Scientific Rationale for Study Design

CCI

population of healthy participants is frequently used in the assessment of the PK of both small and large molecules.

Single 300-mg doses of mirikizumab and the PK sampling time points have been selected to generate PK profiles sufficient to fulfill the study objectives.

Participants will be randomized to receive injections in the arm, thigh, or abdomen, as injection location has been observed to have an impact on bioavailability in some studies with mirikizumab.

Previous population PK analyses have shown that patients with a lower body weight tended to have a lower clearance and/or central volume of distribution. While the effects of body weight on

these PK parameters were statistically significant, it was not considered to be clinically relevant. However, to mitigate these potentially confounding effects, approximately equal numbers of participants in each weight category are proposed to avoid a large difference in mean weight between the test and the reference delivery-device groups. A participant population of 72 per weight group is an approximate target with the recommended weight categories selected based on the distribution of weights in prior studies. The number of participants assigned to each delivery device and the number of participants assigned to each site of injection is desired to be balanced.

A parallel-group design is chosen because mirikizumab has a half-life of approximately 10 days. Additionally, a crossover study could confound PK data if participants develop neutralizing antidrug antibodies (ADAs).

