8.10. Health Economics

This section is not applicable for this study.

9. Statistical Considerations

The statistical analysis plan (SAP) will be finalized prior to first participant first visit and it will include a more technical and detailed description of the statistical analyses described in this section. This section is a summary of the planned statistical analyses of the most important endpoints including primary and key secondary endpoints.

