9.3.2.2. Pharmacokinetic Statistical Inference

The C_{max} , $AUC(0-\infty)$, and $AUC(0-t_{last})$ will be log-transformed and analyzed using a linear fixed-effects model. The model will include delivery device, injection location, and weight stratification as fixed-effects. The dosing regimen differences between AI and PFS administrations will be back-transformed to present the ratios of geometric LS means and the corresponding 90% CI. Comparisons will be made between the 2 delivery devices and then between the 3 injection locations.

The 2 delivery devices will be considered bioequivalent if the 90% CIs of the ratio of geometric LS means fall within 0.8 to 1.25.

The t_{max} of mirikizumab between AI and PFS administrations will be analyzed using a Wilcoxon rank sum test. Estimates of the median difference, 90% CIs, and p-values from the Wilcoxon rank sum test will be calculated.

Additional PK analyses may be conducted if deemed appropriate.

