9.5. Sample Size Determination

Up to approximately 240 participants may be enrolled so that approximately 216 participants (108 in the PFS [reference] group and 108 in the AI [test] group) complete the study.

A sample size of 108 participants per treatment group will provide approximately 90% power that the 90% CI of the geometric mean ratio of C_{max} and AUC between groups will fall within equivalence range of 0.8 to 1.25. This sample size calculation was based on the assumptions that the PK parameters have log-normal distribution, the percent coefficient of variation (CV) of C_{max} and AUC are approximately 40% (based on previous trials), the expected ratio of geometric means is 1.07, and the percent CV are the same for participants from each treatment group.

Participants who are randomized but not administered treatment and participants who do not complete PK sampling through Day 85 may be replaced to ensure that approximately 216 participants (108 in each group) complete the study.

10. Supporting Documentation and Operational Considerations

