#### **9.3.2 Pharmacokinetic Statistical Methodology**

The  $C_{\max}$ ,  $\text{AUC}(0-\infty)$ , and  $\text{AUC}(0-t_{\text{last}})$  will be log-transformed and analyzed using a linear fixed-effects model. The model will include delivery device, injection location, and weight

stratification as fixed-effects. The dosing regimen differences between the AI (Test) and PFS (Reference) administrations will be back-transformed to present the ratios of geometric least squares means and the corresponding 90% CI.

Example SAS Code:

```
proc mixed data=xxx;
by parameter;
class device location strat_weight;
model log_pk = device location strat_weight / residual;
lsmeans device / alpha=0.1 cl pdiff;
ods output lsmeans=lsmeans diffs=diffs;
run;
```

The  $t_{max}$  of mirikizumab between the AI (Test) and PFS (Reference) administrations will be analyzed using a Wilcoxon rank sum test. Estimates of the median difference, 90% CIs, and p-values from the Wilcoxon rank sum test will be calculated.

Additional comparisons will be made between:

- The 2 delivery devices (AI [Test] versus PFS [Reference]) separately at each injection location (injection location will be removed from the model above)
- The 3 injection locations (arm [Test] versus abdomen [Reference] and thigh [Test] versus abdomen [Reference]) separately for each device (device will be removed from the model above)

The 2 delivery devices (AI [Test] versus PFS [Reference]) will be considered bioequivalent if the 90% CIs of the ratio of geometric least squares means of  $C_{max}$ ,  $AUC(0-\infty)$ , and  $AUC(0-t_{last})$  fall within 0.8 to 1.25. CCI

Additional PK analyses may be conducted if deemed appropriate.

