### **11. CHANGES FROM THE PROTOCOL SPECIFIED STATISTICAL ANALYSES**

There were no changes from the protocol specified statistical analyses.

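### The visible text of SAP 9.3.2 compares injection locations only within each device and only against abdomen; the primary model would give all three pairs at half the variance

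*SAP*

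**What the plan says.** Protocol 9.3.2.2 fits one linear model to each log-transformed exposure parameter, with device, location and weight stratum as fixed effects. It then states: "Comparisons will be made between the 2 delivery devices and then between the 3 injection locations". Protocol Section 9 says of the SAP that "it will include a more technical and detailed description of the statistical analyses described in this section".

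SAP 9.3.2 repeats the model. Its example SAS code requests least squares means for device only. It then lists two sets of additional comparisons:

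- AI versus PFS at each location, with location dropped from the model.
- Arm versus abdomen and thigh versus abdomen, "separately for each device (device will be removed from the model above").

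The bioequivalence rule concerns AI versus PFS only. A closing sentence leaves room for further PK analyses without naming any.

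On why location matters, Protocol 2.1 says both devices will be "evaluated at 3 different injection sites (arm, thigh, and abdomen) in order to expand the options for administration in patient use". Protocol 4.2 explains the randomization to site by noting that "injection location has been observed to have an impact on bioavailability in some studies with mirikizumab".

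**The concern.** Location is a randomized factor with three levels, so a comparison between locations has three pairs. The visible SAP text lists two of them, each estimated twice on half the data. Arm versus thigh does not appear. The primary model contains location and will be fitted to all participants, yet no location contrast is requested from it.

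At stake is how precise and complete a secondary result will be. The sites are studied to widen the choice for patients, so the location ratios will be read. As planned, each comes in two versions, one per device, with wider intervals than the data allow. There is no prespecified summary over devices, and no interval at all for arm versus thigh.

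**Working it through.** **Inputs**

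- CV about 40%, expected geometric mean ratio 1.07, limits 0.80 to 1.25, 90% CI, 108 completers per device (Protocol 9.5, SAP Section 7).
- 12 participants per device, location and weight cell (Protocol Table AMBX.1). Over three weight strata this gives 12 × 3 = 36 per device-by-site cell, and 36 × 2 = 72 per site.
- Assumption: the completer target is met and allocation is balanced.

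**1. Log-scale SD.** sqrt(ln(1 + 0.40²)) = sqrt(ln 1.16) = 0.38525.

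**2. The plan's own figure.** SE of the device contrast = 0.38525 × sqrt(2/108) = 0.0524. By normal approximation, the upper limit gives (ln 1.25 − ln 1.07)/0.0524 − 1.645 = 1.32, a probability of 0.907; the lower limit adds almost no loss. The exact two one-sided tests calculation gives 0.905. The stated power of about 90% is reproduced, so the inputs are read as the sponsor used them.

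**3. Location contrast as planned, within one device (36 v 36).** SE = 0.38525 × sqrt(2/36) = 0.0908. Residual df = 108 − 5 = 103. Half-width on the log scale = 1.660 × 0.0908 = 0.1507. Factor = exp(0.1507) = 1.163.

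**4. The same contrast from the primary model (72 v 72).** SE = 0.38525 × sqrt(2/72) = 0.0642. Residual df = 216 − 6 = 210. Half-width = 1.652 × 0.0642 = 0.1061. Factor = exp(0.1061) = 1.112.

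**5. Comparison.** Variance ratio = (0.0642/0.0908)² = 0.50. As an illustration, an observed location ratio of 1.15 would be reported as 0.99 to 1.34 within one device and 1.03 to 1.28 from the primary model. Averaging the two within-device log ratios by hand gives SE 0.0908/sqrt(2) = 0.0642, the same precision, but that average is not a listed result.

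**6. Arm versus thigh within one device.** The point estimate follows by dividing the two listed ratios. The interval does not follow from their two intervals alone, because both ratios share the abdomen group. Requested from the model, its factor is also 1.163.

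**7. Optional: difference in AI/PFS between two sites.** SE of the log ratio of ratios = 0.38525 × sqrt(4/36) = 0.1284. With 208 df, half-width = 0.2122 and factor = 1.236. An observed ratio of ratios of 1.25 would have a 90% CI of 1.01 to 1.55; for 1.40 it would be 1.13 to 1.73.

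**8. Sensitivity to the CV (30% to 50%, an assumed range)**

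| Contrast | CV 30% | CV 40% | CV 50% |
|---|---|---|---|
| Location, within device | 1.122 | 1.163 | 1.203 |
| Location, primary model | 1.084 | 1.112 | 1.139 |
| Ratio of ratios, two sites | 1.175 | 1.236 | 1.297 |

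**The case against.** The best defence is that the SAP already does what the protocol asks. The protocol promises comparisons between three locations without saying pooled, from the single model, or for every pair. Choosing abdomen as reference within each device is the kind of detail a SAP supplies. This stands. A reader might infer that the SAP departs from the protocol and that its Section 11 statement, "There were no changes from the protocol specified statistical analyses", is therefore wrong. The documents do not support that, and Section 11 needs no change.

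A second defence is that within-device contrasts do not assume the same location effect for both devices, whereas the primary model does. This is a fair reason to keep them, but not a reason to leave out the pooled contrast, provided both are shown.

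A reader might also infer that a device effect confined to one site would go unseen. Protocol 2.2.4 reports from an earlier study that in the abdomen "exposure increased by up to 62% following administration using the AI compared to PFS". But AI/PFS ratios at each site are already planned, and the protocol calls that work exploratory and expects similar PK for the two devices. A ratio of ratios is therefore an optional extra. It would also have limited precision: if the true value were 1.25, its 90% CI would exclude 1 with a probability of only about 54%.

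Finally, the SAS code is labelled as an example and also omits contrasts that the SAP does plan, so a missing location line in it proves little. The finding rests on the list of additional comparisons. The clause on further PK analyses permits the missing contrasts but does not prespecify them.

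**Conclusion.** The point holds as a cheap improvement to a secondary analysis, and it is minor. In the visible text of SAP 9.3.2, location is compared only within device and only against abdomen. No arm versus thigh interval is planned, and a contrast with half the variance (factor 1.112 instead of 1.163) is left unreported although its model will be fitted. The figures assume a CV of 40%, 36 completers per device-by-site cell and balance over weight strata.

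The primary bioequivalence conclusion and its power are unaffected, and no visible decision rule depends on location. The finding covers visible text only. Text after the bioequivalence rule in SAP 9.3.2 is redacted, as are parts of the objectives tables and the design rationale, and the TFL shells are not supplied. If the contrasts are specified there, confirming it is enough.

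**What to change.** Keep the primary model, the bioequivalence rule and every planned contrast. In SAP 9.3.2:

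1. Add LSMEANS for location, all three pairs with 90% CIs, from the primary model, and present them beside the within-device contrasts.
2. Add arm versus thigh to the within-device contrasts.
3. Optionally, report the device-by-location ratio of ratios with 90% CI as a descriptive result, without an interaction test deciding which other results are shown.

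The cost is a few lines of code and SAP text, with no new data. The downside is in interpretation: if the device effect differs by site, the location ratio over both devices is only an average, and must be read beside the within-device ratios.

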## 9.4 Safety and Tolerability Assessments

### 9.4.1 Adverse events

Where changes in severity are recorded in the case report form, each separate severity of the AE will be reported in the listings, only the most severe will be used in the summary tables. A pre-existing condition is defined as a condition that starts before the participant has provided written informed consent and is ongoing at consent. A non-treatment emergent AE is defined as an AE which starts after informed consent but prior to dosing. A TEAE is defined as an AE which occurs postdose or which is present prior to dosing and becomes more severe postdose.

All AEs will be listed. TEAEs will be summarized by treatment, injection site, severity and relationship to the study drug. The frequency (the number of AEs, the number of participants experiencing an AE and the percentage of participants experiencing an AE) of TEAEs will be

summarized by treatment, Medical Dictionary for Regulatory Activities (MedDRA) version 24.0 system organ class and preferred term. The summary and frequency AE tables will be presented for all causalities and those considered related to the study drug by the investigator. Any SAEs and product complaints will be listed. Any AEs related to study device will be listed.

Discontinuations due to AEs will be listed.

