2.3. Benefit/Risk Assessment

As with other immunomodulatory therapies, mirikizumab may increase the risk of developing an infection or may exacerbate an existing infection. These may include opportunistic infections and reactivation of latent infections, such as tuberculosis (TB) and hepatitis B, although such infections have not been reported in healthy volunteer clinical trials administering mirikizumab to date. Therefore, participants testing positive for hepatitis B/C, human immunodeficiency virus (HIV), or TB at screening will not be permitted to participate in this study. Immunomodulatory therapies may increase the risk of malignancies; however, due to the single dose of mirikizumab being administered in this study, it is not considered necessary to monitor for such effects.

Immediate hypersensitivity reactions (anaphylactic reaction and infusion-related hypersensitivity reaction), including urticaria, angioedema, and anaphylaxis, have rarely been reported with the administration of mirikizumab.

No other clinically significant safety or tolerability concerns have been identified to date in participants exposed to mirikizumab up to the highest doses given (single 2400-mg IV and SC doses). Of note, the 2400-mg SC dose of mirikizumab was administered in conjunction with human recombinant hyaluronidase as an integral component of the formulation.

Healthy participants are not expected to derive any benefit from participating in studies in which mirikizumab is administered.

As this study will use PFS and AIs, device-based risks will be evaluated based on ISR AEs and bleeding/bruising assessments. Possible device-based risks include local effects such as pain at the injection sites from either the needle or the solution entry into the SC tissue, swelling, erythema, bleeding, and bruising. These risks are mitigated by training of investigative site staff on proper injection techniques. Systemic effects may include sweating, feeling faint, or fever, as a sign of infection.

More detailed information about the known and expected benefits and risks and reasonably expected AEs of mirikizumab may be found in the IB and risks as well as reasonably anticipated adverse device effects of the AI are found in the device IB.

3. Objectives and Endpoints

Objectives	Endpoints
Primary	

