5.4. Screen Failures

Screen failures are defined as participants who consent to participate in the clinical study but are not subsequently enrolled in the study.

Individuals who do not meet the criteria for participation in this study (screen failure) may not be rescreened. Repeating of laboratory tests during the screening period or repeating screening tests to comply with the protocol designated screening period does not constitute rescreening.

6. Study Intervention and Concomitant Therapy

Study intervention is defined as any investigational intervention(s), marketed product(s), placebo, or medical device(s) intended to be administered to/used by a study participant according to the study protocol.

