9.3.3. Safety Analyses

9.3.3.1. Clinical Evaluation of Safety

All study intervention and protocol procedure AEs and PCs will be listed, and, if the frequency of events allows, safety data will be summarized using descriptive methodology.

The incidence of symptoms for each treatment will be presented by severity and by association with study intervention as perceived by the investigator. Symptoms reported to occur prior to study entry will be distinguished from those reported as new or increased in severity during the study. Each symptom will be classified by the most suitable term from the medical regulatory dictionary.

The number of study intervention- and device-related SAEs and any related PCs will be reported.

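### SAP 9.4.1 narrows relatedness from study intervention (which includes the devices) to study drug without declaring it, so no device-related TEAE incidence by device arm is tabulated

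*SAP*

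**What the plan says.** SAP 9.4.1 sets the causality basis twice. For the overview: "TEAEs will be summarized by treatment, injection site, severity and relationship to the study drug". For the tables: "The summary and frequency AE tables will be presented for all causalities and those considered related to the study drug by the investigator". Device attribution is handled in one line: "Any AEs related to study device will be listed". SAEs are also listed.

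Protocol 9.3.3.1 uses a different basis: "The incidence of symptoms for each treatment will be presented by severity and by association with study intervention as perceived by the investigator". The opening of protocol Section 6 defines the term: "Study intervention is defined as any investigational intervention(s), marketed product(s), placebo, or medical device(s) intended to be administered to/used by a study participant". Table AMBX.2 follows that definition, naming the two interventions as mirikizumab in the syringe and mirikizumab in the autoinjector.

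On device risk, protocol 2.3 says that "device-based risks will be evaluated based on ISR AEs and bleeding/bruising assessments".

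SAP Section 3 says that the SAP supersedes the protocol's statistical section and that substantial differences will be identified. SAP Section 11 reports none: "There were no changes from the protocol specified statistical analyses".

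**The concern.** Every participant is to receive 300 mg of the same solution. The main randomised contrast is the device: pre-filled syringe (PFS) against autoinjector (AI). TEAEs and SAEs are the secondary endpoint. The SAP nevertheless plans a relatedness table only for the drug and leaves device attribution to a listing, from which a reader would have to count events by arm.

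The study is also open-label. If investigators divide attribution between drug and device differently for a syringe and an autoinjector, a drug-only table carries that division into the comparison of arms. A table of events related to drug and/or device does not depend on it.

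What is at stake is the completeness and readability of the descriptive safety comparison, and a departure from the protocol that the SAP does not declare.

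**Working it through.** The documents state no related-event rate, so there is no figure to reproduce. The check sets the sections side by side.

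**Step 1. Where each kind of TEAE is counted.** This assumes that drug and device attribution are recorded separately, as the planned device listing suggests.

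| Output | Drug only | Drug and device | Device only |
|---|---|---|---|
| Protocol 9.3.3.1, read with the Section 6 definition | counted | counted | counted |
| SAP 9.4.1 all-causality tables | counted | counted | counted |
| SAP 9.4.1 related tables | counted | counted | **not counted** |
| SAP 9.4.1 device-related AEs | no | listed | listed |
| SAP 9.4.9 ISR summary by treatment | if an ISR | if an ISR | if an ISR |

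The SAP and the protocol differ in one cell, the device-only event in the related tables. No row of the SAP gives a count or percentage of device-related TEAEs by arm.

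**Step 2. Two examples after AI use, each judged due to the device alone.**
- Injection-site erythema: absent from the related tables, but present by treatment in the all-causality tables and the ISR summary.
- Bruising severe enough to be recorded as an AE: absent from the related tables and present in the all-causality tables. It is not among the findings that SAP 9.4.9 names for the ISR summary, and SAP 9.4.11 only lists bleeding and bruising data.

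**Step 3. Device-related SAEs.** Protocol 9.3.3.1 also says that the number of SAEs related to study intervention and to device will be reported. SAP 9.4.1 lists SAEs and lists device-related AEs, and plans no summary of the device-related SAE number.

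**Step 4. Possible size, as illustration only.** Inputs: an ISR frequency of 20.9% in 583 healthy participants (protocol 2.2.3), 108 participants per device group (protocol 9.5), and an assumed share f of ISRs attributed to the device alone, which the documents do not give.

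Participants with an ISR per group: 108 × 0.209 = 22.6. ISR rate left in the drug-related table: 20.9% × (1 − f).

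| f (assumed) | Participants left of 108 | Drug-related table | All-causality table |
|---|---|---|---|
| 0 | 22.6 | 20.9% | 20.9% |
| 0.25 | 16.9 | 15.7% | 20.9% |
| 0.50 | 11.3 | 10.45% | 20.9% |
| 0.75 | 5.6 | 5.2% | 20.9% |
| 1 | 0 | 0% | 20.9% |

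The effect on the related table runs from none to complete, depending wholly on f. The all-causality table does not move.

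**The case against.** The strongest reply is that the SAP follows a usage the protocol itself supports. Protocol 9.3.3.1 names intervention-related and device-related SAEs as two items, and SAP Section 8 equates study intervention with mirikizumab. On that reading, drug-based tables plus a device listing are no departure. This stands in part: the protocol is not consistent. It does not close the gap, because the same protocol sentence calls for a number of device-related SAEs, which the SAP does not plan to summarise. The equation with mirikizumab is the SAP's own and conflicts with protocol Section 6.

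A second reply is that the causality data may not split this way. Protocol 10.3.4 asks the investigator to assess each event against study intervention and describes no separate drug and device questions. If the case report form has one question, the SAP's drug-related field may be that answer and nothing is lost. The TFL shells that could settle this are not part of the documents. This stands, and is why the effect may be zero.

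A third reply is that other outputs already compare the arms: the all-causality tables, the ISR summary and the VAS pain summary (SAP 9.4.10), all by treatment. Protocol 2.3 also ties device risk to ISR AEs and bleeding or bruising, not to a relatedness table. This stands and limits the consequence. Bleeding and bruising data are only listed, however, and none of these outputs gives device-related incidence.

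A reader might go further and infer that related-event rates are miscounted, that they are too low in both arms, or that the table will favour one device. The documents do not support this. A table labelled drug-related counts what it says, and events attributed to both drug and device stay in it. Assuming f = 0.50 for AI and 0.25 for PFS would give 10.45% against 15.7%, but exchanging the two shares reverses the direction, and neither choice has a source. Nor can one say that only device-attributed events could separate the arms: protocol 2.2.4 reports exposure up to 62% higher with the AI than the PFS in the abdomen, so drug-attributed events could differ too.

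**Conclusion.** The point holds in a limited form. SAP 9.4.1 narrows relatedness from study intervention, as protocol Section 6 defines it, to study drug, and SAP Section 11 does not declare it. TEAEs judged related to the device alone are counted by arm only in the all-causality tables and, where they are ISRs, in the ISR summary. No device-related TEAE incidence by device arm is planned.

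The size is unknown and may be nil. It depends on how causality is recorded and on the share attributed to the device alone, neither of which the documents give. The 20.9% used above is itself a loose guide: protocol 2.2.1 describes ISR incidence as highly variable across studies, and this study records only spontaneously reported ISRs (protocol 8.2.5.1).

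Safety is secondary and descriptive, with no inferential analysis planned (SAP 9.4.13). The bioequivalence conclusion is unaffected.

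**What to change.** In SAP 9.4.1:
- Define a related TEAE as one considered related to the drug and/or the device, and base the related summary and frequency tables on that definition beside the all-causality tables.
- Add a tabulation of device-related TEAEs by device arm, with the number of device-related SAEs that protocol 9.3.3.1 calls for.
- Keep the listing of device-related AEs.
- Say which case report form field or fields supply drug and device attribution.

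Reconcile the uses of study intervention in protocol Section 6, protocol 9.3.3.1 and SAP Section 8. If any drug-only basis is kept, declare it in SAP Section 11.

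The cost is wording in the SAP and TFL shells and one or two extra descriptive tables, which may be sparse. The SAP already plans to list device-related AEs, so the attribution data appear to be available. Reported related-TEAE rates may be higher than under the drug-only definition.
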